8.2 STATISTICAL ANALYSIS

The trial results will be reported in accordance with the Consolidated Standards of Reporting Trials (CONSORT). Primary analysis will be intention-to-treat. For our primary analysis, a cox-proportional hazard model will be used to estimate hazard ratio with 95% confidence interval (CI). If the proportional hazard assumption is not valid, we will run a sensitivity analysis by fitting a mixed effects partially proportional hazards regression model with censoring for deaths and loss to follow-up. Although death in ICU may be considered a competing event, censoring for deaths allows us to estimate the instantaneous risk of experiencing a successful extubation event at time t given that the patient is still alive at time t (known as “cause-specific hazard” of extubation for patients who have not yet died). Sites will be included in the model as a random effect, and treatment arm as a fixed effect. For secondary outcomes including quality-of-life measures which are continuous, mixed-effect linear regression models will be used to estimate the treatment effect with 95% CI. For secondary outcomes which are binary, mixed-effect logistic regression models will be used to estimate the treatment effect with 95% CI. We will explore different approaches that allow incorporation of multiple relevant outcomes including death into a single overall measure (e.g., win ratio [18]). A detailed statistical analysis plan will be agreed with the data monitoring committee.

8.3 SUB-GROUPS

We will examine the following subgroups:

- Neurological condition as the primary reason for ICU admission
- Duration of ventilation prior to randomisation: <48 hours and ≥48 hours; <7 days and ≥7 days;
- Mode of ventilation at randomisation: Controlled/Mandatory mode versus spontaneous mode

These subgroup analyses will be performed using intention to treat. We will use the primary outcome as the dependent variable and interaction with treatment and sub-group. We will use linear regression models to assess the subgroup effect, using interaction terms. As these analyses are post-hoc analyses not powered for any effect size. Emphasis will be placed on the point estimates and 95% CIs, rather than the statistical testing.

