3.4.1 PRIMARY OBJECTIVE AND OUTCOME

Our primary objective is to determine the effectiveness of NAVA technology for reducing the duration of mechanical ventilation compared to conventional IMV.

Our primary outcome is duration of mechanical ventilation in days commencing at randomisation and discontinuing at first successful unassisted breathing or death.

Successful unassisted breathing is defined as breathing unassisted at 48 hours with no inspiratory support or extracorporeal lung support. Duration of assisted breathing includes time receiving extracorporeal lung support, invasive mechanical ventilation and non-invasive ventilation delivering volume or pressure support ventilation; **excludes** high-flow oxygen therapy and continuous positive airway pressure.

This definition was agreed through an international consensus process, involving clinician, researcher, patient and family representatives, and industry [17]. This primary outcome was chosen with Public and Patient Involvement (PPI) input.

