8 STATISTICS AND HEALTH ECONOMICS

8.1 SAMPLE SIZE CALCULATION

The trial will recruit a total of 900 (450 per arm) participants (using 90% power, 5% significance level, and 5% loss to follow-up) to detect effect size of 2-days reduction in duration of MV. The parameter estimates for this study have been derived as follows:

1. **Effect size of 2-days reduction:** Given previous meta-analyses [12-14] showed a reduction of MV duration with NAVA Technology of between 2.6 and 4.9 days, an effect size of 2 days is conservative and can be realistically achieved.
2. **Median duration of ventilation on the control arm:** Reported MV duration varies from 7 to 14 days in UK studies (i.e., 4.5 days- BREATHE study [32]; 14.1 days -OSCAR trial [33]). Amongst patients ventilated >48 hours (UK NAVA inclusion criteria), a commissioned report on 2018 and 2019 ICU admissions (ICNARC) and a recent, large international study [34] (Weansafe, Lancet Respiratory, May 2023) found median (IQR) MV durations of 6 days (4 to 11) and 7 days (4 to 12) respectively. To allow for any uncertainties and differences in the population, we have taken a more conservative estimate of 10 days for our sample size calculations.
3. **Loss to follow-up:** In the previous ICU studies, loss to follow-up ranges from 0% to 3% (1.1% - BREATHE [32]; 0% - OSCAR [33]; 0.4% - HARP-2 [35]; 3% - REST [36]). We have used a conservative estimate of 5% as our loss to follow-up rate.

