8.4 FUTILITY ANALYSES

The methods for futility analyses and determining futility boundaries which account for censored observations are very limited in the literature. Assuming there is no censoring (and for every patient, an event will be observed), we can use normal approximation methods for the log hazard ratio. This assumption is reasonable in the context of this study. In consultation with the DMC, we aim to plan for a futility analysis halfway through our trial (at 50% sample size). We will use the conventional conditional power boundaries at this interim point, where we will declare for futility if the conditional power is <15%. Assuming our hazard ratio is 1.25 (as per the sample size), this interim analysis (and boundaries) does not impact on the overall study power of 90%. This futility rule will be used as a guidance criterion by the DMC. The decision to stop will be based largely on clinical judgement of all the outcomes, as well as parameters that drive operational futility (recruitment).

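### Section 8.3 assigns linear regression in days to subgroup effects on a primary outcome that is otherwise analysed by Cox regression, and gives no reason for the change of scale

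*Protocol*

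**What the plan says.** Protocol section 8.3 lists subgroups by neurological reason for admission, by ventilation time before randomisation (two splits), and by ventilation mode at randomisation. On method it states "We will use the primary outcome as the dependent variable and interaction with treatment and sub-group" and then "We will use linear regression models to assess the subgroup effect, using interaction terms". It continues "As these analyses are post-hoc analyses not powered for any effect size", and says that estimates and intervals will carry more weight than tests.

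The outcome concerned is defined in section 3.4.1 as "duration of mechanical ventilation in days commencing at randomisation and discontinuing at first successful unassisted breathing or death". Elsewhere it is handled on the hazard scale:

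- Section 8.2, primary analysis: "a cox-proportional hazard model will be used to estimate hazard ratio with 95% confidence interval (CI". Site is a random effect. The model held in reserve for non-proportional hazards is described "with censoring for deaths and loss to follow-up", with a cause-specific-hazard rationale. Linear models appear in 8.2 only for continuous secondary outcomes.
- Section 8.4, futility: a normal approximation for the log hazard ratio, "Assuming our hazard ratio is 1.25 (as per the sample size".
- Section 8.1, sample size: 900 patients "to detect effect size of 2-days reduction in duration of MV", from a control median of 10 days with 5% loss to follow-up.

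**The concern.** This is a stated choice of model, not a detail left for later. An analysis plan that follows section 8.3 inherits the mismatch, and one that departs from it contradicts the protocol.

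Three consequences follow. First, a subgroup effect in days cannot be read against a primary result reported as a hazard ratio. Second, ordinary linear regression needs a complete duration for every patient. It has no provision for the losses that section 8.1 allows, or for the deaths that section 8.2 discusses censoring. Third, a treatment that multiplies the hazard by the same factor everywhere saves more days where ventilation lasts longer. A linear interaction can then appear when the hazard ratio does not vary, and readers may take it as evidence that the treatment works differently across subgroups.

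**Working it through.** **The plan's own figure.** Inputs from sections 8.1 and 8.4: hazard ratio 1.25 (10/8 = 1.25), 90% power, 5% significance (sidedness not stated; two-sided assumed), 5% loss, 1:1 allocation.

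- Schoenfeld events: 4 × (1.960 + 1.282)² / (ln 1.25)² ≈ 844.1, so 845. Divided by 0.95, this gives 890 patients.
- Freedman events: (2.25/0.25)² × (1.960 + 1.282)² ≈ 851, so 852. Divided by 0.95, this gives 897 patients.

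Both agree with 900. The trial is therefore sized on a hazard ratio, with an event assumed for every patient followed.

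**Days saved under a common hazard ratio.** Assume exponential times with control median m. The control mean is m/ln 2 and the treated mean is (m/1.25)/ln 2, so the mean reduction is

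m × (1 − 1/1.25) / ln 2 = 0.2m / 0.693 = 0.2885m.

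This gives 1.30 days for m = 4.5, 1.73 for 6, 2.02 for 7, 2.89 for 10, 4.04 for 14 and 4.07 for 14.1. The linear interaction is the difference between two such values. For 6 v 14 it is 4.04 − 1.73 = 2.31 days.

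The protocol gives no subgroup medians. The pairs below are assumptions within the 4.5 to 14.1 days that section 8.1 quotes from UK studies.

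**Simulation.** The set-up was 855 patients (900 × 0.95), 1:1 arms, a 50:50 subgroup split, hazard ratio 1.25 in both subgroups, exponential times, and no censoring. There were 1,000 trials per pair, except that the 7 v 10 row comes from separate runs of 800 and 2,000 trials. Two-sided 5% tests were used.

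| Control medians (days) | Interaction in days (formula) | Linear interaction significant | Cox interaction significant |
|---|---|---|---|
| 10 v 10 | 0 | 5% | 5% |
| 7 v 10 | 0.87 | 9% | 6% |
| 6 v 10 | 1.15 | 12% | 5% |
| 7 v 14 | 2.02 | 18% | 6% |
| 6 v 14 | 2.31 | 22% | 5% |
| 4.5 v 14.1 | 2.77 | 32% | 6% |

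Robust standard errors leave the linear rates almost unchanged. With Weibull times of shape 1.3, the simulated interactions for the last three pairs are about 1.3, 1.5 and 1.9 days, and the linear rates are 16%, 21% and 31%. Cox rates there are 4 to 5%. The mean Cox interaction is within 0.01 of zero on the log scale in every pair run with 1,000 trials.

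**The case against.** The strongest reply is that days are a legitimate scale. The target effect and the economic argument in section 8.5 are both expressed in days. With a common hazard ratio and unequal durations, the benefit in days truly differs, so the 22% is power to detect a real additive difference. The converse also holds. A 2-day saving in the median in both subgroups would mean hazard ratios of 6/4 = 1.50 and 14/12 = 1.17 under exponential times, and Cox would show an interaction. This part stands: a reader might infer that linear regression produces false positives or spurious effect modification, and the protocol does not support that. What remains is that 8.3 does not say it wants the additive scale, while the trial reports a hazard ratio.

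Three other strong readings also fail:

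- *The subgroups differ in duration by construction.* They are split on ventilation before randomisation or on mode at randomisation, while the outcome clock starts at randomisation. Different durations are plausible, not built in.
- *Linear regression is at fault for counting an early death as a short duration.* Section 3.4.1 itself ends the duration at death, so a Cox model on that endpoint would do the same.
- *The two splits of prior ventilation time are an error.* Recoding them as one factor is a preference.

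On censoring, section 8.4 regards an assumption of none as reasonable, and section 8.1 cites losses of 0% to 3% in earlier studies. Section 8.2 mentions censoring deaths only for the reserve model and its rationale. The gap in the linear model is real but probably small for losses. The difference in days above arises with no censoring at all.

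Finally, 8.3 plays down testing. That lessens the consequence, but the point estimate in days is itself what shifts.

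**Conclusion.** The mismatch stands. Section 8.3 names a model and scale that differ from the primary analysis, the sample size and the futility rule, and does not justify the change. Under a common hazard ratio of 1.25 and exponential times, the resulting interaction ranges from none (equal medians) through about 0.9 days (7 v 10) and 2.3 days (6 v 14) to 2.8 days (4.5 v 14.1). The corresponding rejection rates are about 5%, 9%, 22% and 32%, against about 5% for Cox. The larger values exceed the trial's 2-day target effect.

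These sizes rest on assumed subgroup medians, an even subgroup split and simple time distributions. They show what could happen, not what will. Calling subgroups that the protocol lists in advance *post hoc* is a separate wording slip. Because the analyses are exploratory and unpowered, this is a change worth making but at the low end of importance. The primary result is unaffected.

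**What to change.** In section 8.3, replace linear regression with the primary Cox model, including the site random effect, plus a treatment-by-subgroup interaction. Report the hazard ratio in each subgroup and the ratio of hazard ratios, each with a 95% confidence interval. An effect in days may be added as a supplementary summary, labelled as additive-scale. Describe the analyses as pre-specified and exploratory instead of post hoc.

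The subgroup model should use the same event definition and handling of death as the primary analysis. That requires section 3.4.1, where death ends the outcome, to be reconciled first with section 8.2, where censoring deaths is discussed. Apart from that step, the cost is two sentences of wording, with no extra patients or data.

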8.4 FUTILITY ANALYSES

The methods for futility analyses and determining futility boundaries which account for censored observations are very limited in the literature. Assuming there is no censoring (and for every patient, an event will be observed), we can use normal approximation methods for the log hazard ratio. This assumption is reasonable in the context of this study. In consultation with the DMC, we aim to plan for a futility analysis halfway through our trial (at 50% sample size). We will use the conventional conditional power boundaries at this interim point, where we will declare for futility if the conditional power is <15%. Assuming our hazard ratio is 1.25 (as per the sample size), this interim analysis (and boundaries) does not impact on the overall study power of 90%. This futility rule will be used as a guidance criterion by the DMC. The decision to stop will be based largely on clinical judgement of all the outcomes, as well as parameters that drive operational futility (recruitment).

8.5 HEALTH ECONOMIC EVALUATION

We will undertake a full health economic evaluation. Reduced duration of mechanical ventilation may reduce ventilator-associated co-morbidities and hospital service resource use compared to usual care. The cost of a Level 3 (ICU) bed day in critical care (based on 2 to 6 organs being supported) is approximately £1,900 [20]. If the use of NAVA Technology results in patients coming off mechanical ventilation two days earlier and stepping down to a lower level of care, this could save more than £1000 per patient with ARF (based on a Level 2 (High Dependency Unit) bed day cost of £1136) [20]. This is a conservative estimate of the economic saving because their overall hospital length of stay may also be reduced. We will assess the cost-effectiveness of the different groups compared with usual care at 6 months via a cost-utility analysis. We will follow NICE methodological guidance in taking the perspective of the NHS and personal social services for the analysis [21]. The cost per quality adjusted life year (QALY) gained and the net benefit for NAVA Technology compared to usual care will be estimated.

A within-trial analysis will be conducted to assess the cost-effectiveness of NAVA Technology and usual care at 6 months. Information about patients' use of healthcare and social care services within the trial period will be collected using a recently developed costing questionnaire that will be adapted for use in this trial [22]. We will include the minimum set of core resource use items recommended for UK economic evaluations [21]. These include:

- Hospital care - Number of inpatient or day-case hospital admissions; length of stay; number of hospital outpatient appointments
- Emergency care – Number of visits to Emergency Departments; number of admissions to hospital, after a visit to the Emergency Department
- Care at a GP surgery, health clinic, or other community setting – Number of appointments; type of professional seen

For those patient subgroups where the results of within-trial analyses suggest that NAVA Technology is likely to have a long-term impact on people's outcomes, economic modelling will be used to extrapolate

the trial data over a lifetime horizon, if the budget allows. The selection of patient subgroups for modelling will be guided by (a) the level of uncertainty regarding the conclusions of the six-month trial-based economic analysis (with priority given to those patient subgroups with a greater level of uncertainty); and (b) the availability of data to support model development. Model development will depend heavily on the research question [23] and thus, the model type will be determined in the course of the milestones-dependent project. However, we anticipate that this may involve the development of 1–2 decision-analytic Markov models [24]. Within a Markov model, events are modelled as transitions from one health state to another over time. The time period of the model is divided into cycles of time, for example a year, and at each cycle, there is a probability of remaining in the same state or progressing to a different state within the model.

Patient's use of the Social care service – Number of appointments with a social worker, or care worker QALYs will be calculated using utilities generated from EQ-5D-5L responses at the point of consent to continue (in lieu of a baseline measure), 60 days, and 6 months. Uncertainty in the data will be summarised in cost effectiveness acceptability curves showing probability of the treatment strategies being cost-effective at different threshold levels of willingness-to-pay per QALY. Sensitivity analysis will be performed to explore impact on cost effectiveness of variations in key parameters. Further details and full descriptions of analyses will be given in the Health Economics Analysis Plan.

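### Section 8.5 lets observed subgroup results decide which patients enter the optional lifetime economic model and states no whole-population lifetime model, so any extrapolated effect is likely to be exaggerated

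*Protocol*

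**What the plan says.** Section 8.5 of the protocol describes two layers of economic work.

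- **Within-trial:** "A within-trial analysis will be conducted to assess the cost-effectiveness of NAVA Technology and usual care at 6 months". Entry to this analysis does not depend on any result.
- **Lifetime:** modelling is proposed "For those patient subgroups where the results of within-trial analyses suggest that NAVA Technology is likely to have a long-term impact". For those subgroups the model would extrapolate "the trial data over a lifetime horizon, if the budget allows".

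The choice of subgroups is then guided by two further criteria. One is uncertainty about the six-month economic conclusions, "with priority given to those patient subgroups with a greater level of uncertainty". The other is "the availability of data to support model development". One or two Markov models are anticipated, and fuller detail is left to the Health Economics Analysis Plan.

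No direction, effect measure or threshold is given for what counts as a long-term impact. No lifetime model for all randomised patients is mentioned. Section 8.3, the only place that lists subgroups, describes its analyses as "post-hoc analyses not powered for any effect size".

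**The concern.** The data that decide whether a subgroup is modelled are the same data that feed the model. A subgroup enters because its estimate looks large enough to matter in the long run, and part of that size is chance. The lifetime model then projects the chance component over decades. Acceptability curves and sensitivity analyses centred on the selected estimate do not remove this, because they describe spread around a value that is already displaced.

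The research question in section 2.4 concerns all patients at risk of difficult or prolonged weaning. If the rule is followed as written, the only lifetime estimates would describe subgroups picked on their results. A decision maker looking for a lifetime cost per QALY would have no figure for the trial population to set beside them.

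**Working it through.** **Inputs from the protocol.** Section 8.1: 900 patients (450 per arm), 90% power, 5% significance (taken as two-sided), 5% loss to follow-up, control median 10 days, reduction of 2 days. Section 8.4: hazard ratio 1.25, with an event assumed for every patient. A ratio above 1 means earlier liberation from ventilation with NAVA.

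**Reproducing the sample size.** The ratio is 10/8 = 1.25.

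- Schoenfeld: events = 4(1.960 + 1.282)² / (ln 1.25)² = 845 after rounding up; 845/0.95 = 890.
- Freedman: events = (1.960 + 1.282)² × (2.25/0.25)² = 852 after rounding up; 852/0.95 = 897.

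Both agree with 900 to within 3%. The analysable number is 0.95 × 900 = 855 events, which gives 90.4% power.

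**Assumptions.** The protocol gives no subgroup sizes and no variances for costs or utilities. I therefore take subgroups holding 50%, 25% and 10% of the 855 events, and use the ventilation hazard ratio as a stand-in for benefit.

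**Formula.** The estimated log hazard ratio is approximately normal with mean m (the true value) and standard error s = 2/√events. If a subgroup is modelled only when its estimate exceeds a cut-off c, the expected carried-forward estimate is m + s·φ(a)/(1 − Φ(a)), where a = (c − m)/s. Results are exponentiated.

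| Share (events) | s | True 1.00, any estimate > 1 | True 1.00, estimate > 1.25 (chance of selection) | True 1.25, any estimate > 1 | True 1.25, estimate > 1.25 |
|---|---|---|---|---|---|
| 50% (428) | 0.097 | 1.080 | 1.292 (1.1%) | 1.253 | 1.350 |
| 25% (214) | 0.137 | 1.115 | 1.324 (5.1%) | 1.269 | 1.394 |
| 10% (86) | 0.216 | 1.188 | 1.398 (15.1%) | 1.327 | 1.485 |

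Worked example, 10% share, true ratio 1.00, any favourable estimate: a = 0, φ(0)/0.5 = 0.798, 0.216 × 0.798 = 0.173, exp(0.173) = 1.19.

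**Either direction qualifies.** Suppose a subgroup enters if its estimate is above 1.25 or below 0.80. With a true ratio of 1.00 the average is 1.00, so there is no net tilt towards NAVA. But the subgroups that enter on the favourable side average 1.292, 1.324 and 1.398, and those on the unfavourable side average the reciprocals (1/1.292 = 0.77, 1/1.324 = 0.76, 1/1.398 = 0.72). Each is wrong, in one direction or the other.

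**Effect of the priority rule.** Down every column, the noisier the estimate the larger the exaggeration. Under the 1.25 cut-off with no true effect, noisier subgroups are also selected more often. To the extent that greater uncertainty reflects a less precise estimate, ranking entrants by uncertainty favours the subgroups where selection does most harm.

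**The case against.** Several points on the other side stand.

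- **Direction.** A reader might infer that the plan models only subgroups that look favourable, so that the lifetime result must be biased towards NAVA. The text does not say so: it speaks of impact, and apparent harm would also qualify. Benefit is a natural reading, because section 8.5 opens with expected savings, but it remains a reading.
- **No pick-the-best rule.** Nothing in 8.5 selects the most favourable subgroup. Calculations on the maximum of several subgroup estimates show multiplicity in general, not this rule, and I do not rely on them.
- **The further criteria.** Data availability is neutral. Uncertainty about an economic conclusion is, for a given precision, greatest near the decision threshold, which could steer away from a striking subgroup. That partly offsets the concern about precision, but both criteria apply to subgroups that already met the results-based condition.
- **Which subgroups.** Section 8.5 does not say that its subgroups are those of 8.3, and 8.3 concerns the primary outcome only. No other subgroups are listed, however, and none is shown to be better powered.
- **Scope.** The lifetime work is optional and budget-dependent, and the 6-month analysis stands apart from it.
- **Deferral.** Direction, threshold and model structure may properly go to the Health Economics Analysis Plan, which is not shown. But the results-based entry condition is itself in the protocol, so a plan faithful to the protocol would inherit it.

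**Conclusion.** The point holds within limits. As written, section 8.5 makes lifetime modelling depend on observed subgroup results, favours the more uncertain subgroups, and states no lifetime model for the randomised population. Carrying such estimates forward without correction exaggerates the effect.

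The direction is conditional. The bias is towards NAVA if impact means benefit. If either direction counts and NAVA has no effect, the average bias is nil while each selected estimate is still overstated. The size also depends on the cut-off. Under a lenient rule with the planned effect true, the distortion is small in large subgroups (1.253 against 1.25). With no true effect, or a strict rule, it is material.

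These figures rest on assumed subgroup shares and on the ventilation hazard ratio as a proxy. They illustrate the mechanism and do not estimate bias in cost per QALY, for which the protocol lacks the inputs. A reader might also infer that the trial's main cost-effectiveness answer is compromised. It is not: the 6-month within-trial cost-utility analysis is not selected on results.

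**What to change.** In section 8.5, and in the Health Economics Analysis Plan, state that if lifetime modelling is done, its base case is the whole intention-to-treat population. Limit any subgroup lifetime models to subgroups named before outcome data are seen, chosen by criteria that do not depend on observed results (data availability can stay), and label them exploratory.

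Because the wording is conditional, it does not turn budget-dependent work into a commitment. It needs no extra data and no change to the 6-month analysis. The cost is that one of the one or two anticipated models is used for the whole population, and there is less freedom to pursue a striking subgroup.

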	
 3. Reintubation 4. Use of non-invasive ventilation following extubation 5. ICU and hospital length of stay 6. Serious adverse events up to hospital discharge 7. Health related quality of life (EQ-5D-5L) at 2 months and 6 months after randomisation 8. Acute health care use at 6 months following randomisation 
We will conduct a within-trial cost-utility analysis from an NHS hospital care perspective

Statistical methods	
 1. Primary analysis will be intention-to-treat. 2. Primary analysis: Cox proportional hazard regression model will be used to estimate the treatment effect reporting hazards ratio and its 95% confidence interval (CI), using both unadjusted and adjusted analysis. 3. Secondary analysis: Random effects models will be used depending on distribution of the outcomes. The unadjusted and adjusted treatment effects and its 95% CI will be reported.

DRAFT

Abbreviations / glossary

Table 2. Abbreviations / glossary

ARDS	Acute Respiratory Distress Syndrome
CI	Confidence Intervals
COPD	Chronic Obstructive Pulmonary Disease
CoReCCT	Confederation of Respiratory Critical Care Trials
eCRF	Electronic Case Report Form
EDi	Electrical diaphragmatic activity measured in microvolts
ETT	Endotracheal tube
DMC	Data Monitoring Committee
HRQoL	Health-related Quality of Life
ICU	Intensive Care Unit
IMV	Invasive Mechanical Ventilation
ISRCTN	International Standard Registered Clinical/soCial sTudy Number
NAVA	Neurally Adjusted Ventilatory Assist
NAVA Technology	Diaphragm monitoring plus the NAVA ventilation mode
NIV	Non-invasive ventilation
PEEP	Positive-end expiratory pressure
PPI	Public and Patient Involvement
PSV	Pressure Support Ventilation
QALY	Quality Adjusted Life Year
RCT	Randomised Controlled Trial
RASS	Richmond Agitation Sedation Scale
R&D	Research and Development
REC	Research Ethics Committee
SAE	Serious Adverse Event
TMG	Trial Management Group
TSC	Trial Steering Committee
Vt	Tidal Volume

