3.7 CONSENT

It is the responsibility of each site Principal Investigator (PI) (or designee) to ensure that written informed consent is obtained for each participant prior to entry into the trial. Consent may be obtained by the PI, or an appropriately trained member of the site team provided they are GCP trained, suitably qualified and experienced and have been delegated this duty by the PI on the delegation log.

Eligible patients will be unable to give informed consent because of sedation and IMV. In most cases (in England, Wales and Northern Ireland), it is expected that advice will be sought from an appropriate consultee prior to randomisation. In some circumstances, where there is a limited window of opportunity to insert an NAVA catheter, it may not be possible to seek prior assent from an appropriate consultee prior to randomisation. Opportunities for NAVA catheter insertion commonly occur in the early acute phase of illness, when patients are sedated. This reduces patient discomfort due to the existing sedation and analgesia, and reduces the risks involved in nasogastric/orogastric tube removal and replacement. For these reasons, we will seek approval from a research ethics committee to use a deferred consent model. For sites in Scotland, it is expected that advice will be sought from an appropriate Welfare Guardian/Nearest Relative. In cases where no Welfare Guardian/Nearest Relative is available it will not be legally possible to enrol the participant (specific to the Adults with Incapacity Act Scotland for non-CTIMP trials).

Once a participant who initially lacks capacity, regains capacity, they will be informed about the trial and invited to consent to continue in the trial. There is no requirement to reaffirm consent in Scotland.

Further details on the consent process are detailed in section 4.2.3 of the CoReCCT master protocol.

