5.1 TRIAL PROCEDURES SCHEDULE

Table 4. Data collection schedule

	Baseline	Up to ICU dx	Up to hospital dx	2 months	6 months
Screening for eligibility	X				
Informed consent	X				
Baseline data collection	X				
Randomisation	X				
Ventilator settings, sedation use, organ failure		X			
Adverse events		X	X		
Primary & secondary outcomes		X			

Mortality (secondary outcome)		X	X	X	X
HrQoL (secondary outcome)				X	X
Healthcare utilisation after dx				X	X

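### The stand-in baseline utility for QALYs is a post-randomisation, selectively available EQ-5D-5L that can bias the QALY difference, and the protocol states two different cost perspectives

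*Protocol*

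**What the plan says.** **Utility.** Protocol section 8.5 states: "QALYs will be calculated using utilities generated from EQ-5D-5L responses at the point of consent to continue (in lieu of a baseline measure"), with further measurements at 60 days and 6 months. Section 3.7 explains why there is no true baseline: "Eligible patients will be unable to give informed consent because of sedation and IMV". When capacity returns, "they will be informed about the trial and invited to consent to continue in the trial". For Scotland the same section adds: "There is no requirement to reaffirm consent in Scotland". Section 3.11 says that quality of life is the one outcome needing self-report.

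**Schedule.** Table 4 in section 5.1 has one quality-of-life row, "HrQoL (secondary outcome"), marked at 2 and 6 months. Table 1 and section 3.4.2 give the same two time points. None of the three shows a measurement at consent to continue.

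**Perspective.** Table 1 describes a "within-trial cost-utility analysis from an NHS hospital care perspective", and section 3.4.2 repeats this. Section 8.5 instead speaks of "taking the perspective of the NHS and personal social services for the analysis", and lists GP, community and social care contacts among the resource items.

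**Deferred detail.** Section 8.5 leaves the full description of the analyses to a Health Economics Analysis Plan, which is not at hand.

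**The concern.** A baseline utility should be fixed before treatment can act and should exist for everyone randomised. The substitute has neither property. It is measured when the patient wakes and regains capacity, and that moment plausibly depends on time on the ventilator, which is what NAVA is meant to shorten. It exists only for patients who reach that point and are asked.

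Three natural ways of using it could distort the QALY difference:

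- entering it at day 0, which removes the time spent ventilated from the QALY total;
- adjusting for it as a baseline covariate, which can remove part of a treatment effect;
- requiring it in a complete-case analysis, which leaves out patients who died before they could be asked.

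The two perspectives raise a different question: which costs count. Hospital-only costs and NHS plus personal social services costs generally give different incremental costs and so different net benefits.

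**Working it through.** **The plan's own figure.** The protocol gives no utility, QALY or cost-effectiveness calculation to reproduce. The nearest figure is the projected saving in section 8.5 of more than £1000 per patient. Its bed-day costs are about £1,900 (Level 3) and £1136 (Level 2), so two days give 2 × (1900 − 1136) = £1,528, consistent with that statement.

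**1. Timing: the consent-time value entered at day 0.** All of these inputs are assumptions:

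- capacity regained at day 14 (control) and day 12 (NAVA), so that the planned 2-day effect carries over to waking;
- utility while ventilated, u0, from −0.4 to 0;
- utility at consent, uc, from 0.1 to 0.5, the same in both arms;
- utility at 60 days, u60, from 0.5 to 0.6.

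QALYs over 60 days with the value at day 0: 60 × (uc + u60)/2 ÷ 365.

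QALYs with the value at its true day t: [t × u0 + (60 − t) × (uc + u60)/2] ÷ 365.

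Overstatement = t × [(uc + u60)/2 − u0] ÷ 365.

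- Smallest case (u0 = 0, uc = 0.1, u60 = 0.5): control 14 × 0.30/365 = 0.0115; NAVA 12 × 0.30/365 = 0.0099; NAVA minus control −0.0016.
- Largest case (u0 = −0.4, uc = 0.5, u60 = 0.6): control 14 × 0.95/365 = 0.0364; NAVA 12 × 0.95/365 = 0.0312; NAVA minus control −0.0052.

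The control arm gains more because it has more ventilated days to erase, so the error runs against NAVA. At an assumed £20,000 per QALY it is worth £33 to £104; at an assumed £30,000, £49 to £156. Both are small beside £1,528.

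**2. Missing values.** Assume that 20% to 40% die before regaining capacity and that 0% to 10% of participants are in Scotland, with none of the latter measured. The share without a value is 1 − (1 − d)(1 − s):

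- low: 1 − 0.8 × 1.0 = 20%, or 180 of 900;
- high: 1 − 0.6 × 0.9 = 46%, or 414 of 900.

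A complete-case analysis that needs this value drops the mortality part of the QALY difference. With an assumed 0.2 to 0.3 QALY per survivor over the trial, a 5-point mortality difference is worth 0.05 × 0.2 = 0.010 to 0.05 × 0.3 = 0.015 QALY. A 2-point difference is worth 0.004 to 0.006.

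**3. Covariate adjustment.** If the consent-time utility differs between arms by δ because of treatment, and predicts QALYs with slope b, adjustment removes b × δ. With assumed b of 0.2 to 0.3 and δ of 0.02 to 0.10, that is 0.004 to 0.030 QALY. Nothing in the protocol supports a particular δ.

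**4. Perspective.** No arithmetic applies. Table 1 and section 3.4.2 restrict the analysis to hospital care. Section 8.5 widens it to personal social services and collects matching GP, community, social worker and care worker contacts. One base case cannot satisfy both.

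**The case against.** The strongest reply is that section 8.5 names only the sources of the utilities. It does not say that the first value sits at day 0, serves as a covariate or defines the analysis set, nor how deaths are valued. Those rules normally belong in the Health Economics Analysis Plan, and section 8.5 promises sensitivity analyses. Using the measure as an intermediate point with death at 0 would fit the text as written. This stands: a reader might infer that the cost-utility result is biased, but the protocol does not establish that.

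Three other strong readings also fail.

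- A reader might set the per-patient overstatement of about 0.010 to 0.036 QALY against the projected saving. The first is a shift in level that largely cancels between arms; the second is a between-arm difference.
- A reader might conclude that Scottish participants cannot have this measurement. Section 3.7 says only that re-consent is not required there. It does not bar an EQ-5D-5L, and the number of Scottish sites is not given.
- A reader might say that the intended base case cannot be told. Section 3.4.2 points forward, and section 8.5 gives one perspective with matching resource items, so it can be inferred. The summary and the objectives still contradict it.

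On the schedule, Table 4's row is labelled as the secondary outcome, and sections 5 and 5.2 send core data and follow-up procedures to the CoReCCT master protocol, which is not at hand. The measurement may be scheduled there. It remains absent from this protocol's own schedule, although section 8.5 relies on it.

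**Conclusion.** The point holds as a risk of bias and as a contradiction to be reconciled. Certain from the text: the substitute for a baseline is post-randomisation, obtainable only from patients who regain capacity, and absent from Table 4 and the outcome lists; and two cost perspectives are stated.

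The overall size and direction of any bias cannot be fixed from the protocol. On the assumed inputs the timing part is about 0.002 to 0.005 QALY against NAVA, which is small. Missing values could matter more, at 0.010 to 0.015 QALY for an assumed 5-point mortality difference under complete-case analysis. All of this depends on handling that the Health Economics Analysis Plan may settle. It cannot, however, agree with both stated perspectives. Since cost-effectiveness is a named aim (sections 3.4 and 3.4.3), the correction is worth making.

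**What to change.** - **Perspective.** State NHS and personal social services as the base case in Table 1 and section 3.4.2, to match section 8.5, with hospital-only costs as a sensitivity analysis.
- **Starting utility.** In section 8.5, assign the same fixed utility at randomisation to every participant in both arms, and vary it in sensitivity analysis.
- **Deaths.** Value death at 0 from the date of death.
- **Consent-time EQ-5D-5L.** Add it to Table 4 and use it only as an intermediate value at its actual date, not as a baseline value or covariate. State how missing values are handled, including where no re-consent contact takes place.

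The cost is wording in the protocol and the Health Economics Analysis Plan. The downside is that the common starting utility is an assumption, which is why it needs the sensitivity analysis.
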